7.2.3.1. Humoral immune response

Within group evaluation

For each group, at each time point during which blood samples are collected for humoral immune response and for each assay:

- Seropositivity rate and their exact 95% CI will be tabulated.
- GMCs and their 95% CI will be calculated.
- Antibody concentrations distribution will be investigated using Reverse Cumulative Curves.

These analyses will also be performed for each level of the following minimisation factors: age (50-59 years vs. 60-70 years), smoking status (current vs. former smoker), FEV₁/FCV ratio (≥ 0.7 vs. < 0.7).

Between groups evaluation (only for Step 2)

Comparative analyses will be exploratory with the aim to characterise the difference between the 10-10-10-AS and 10-10-3-AS groups in humoral immune response.

The difference in terms of GMCs will be evaluated, one month post-Dose 2, by computing the 95% CIs of the GMC ratio between groups for Step 2 by using a one-way ANCOVA model on the logarithm10 transformation of the concentrations/ titres. The ANCOVA model will include the group category, the age category, the smoking status and FEV₁/FVC (≥ 0.7 or < 0.7) and the pre-Dose 1 concentration (as co-variable) as fixed effects. The groups will be considered significantly different if the 95% CI for the GMC ratio between the two groups does not contain the value 1.

Study alias & e-track number(s): NTHI MCAT-001 (201281)

However, these differences should be interpreted with caution considering that there will be no adjustment for multiplicity of endpoints.

7.2.3.2. CMI response

The frequency of specific CD4⁺/ CD8⁺ T-cells will be summarised (mean, SD, minimum, Q1, median, Q3, and maximum) by group, at each time point during which blood samples are collected for CMI (descriptive statistics).

Each data will be obtained by subtracting the summary of the background value to each summary value. Values less than or equal to zero will be set to 1 for the purpose of geometric mean calculation and graphical representation.

7.2.3.3. Summary score to support dose selection

The calculation of a summary score for both active groups of Step 2 (i.e. 10-10-10-AS and 10-10-3-AS) will be proposed in order to help the formulation selection. The group(s) with the highest summary score(s) should potentially be the one(s) considered for selection provided it (they) has (ve) an acceptable safety and CMI profile. However note that a difference of less than 0.02 between 2 summary scores will not be sufficient to consider that a formulation should be ranked higher than/preferred to the other.

Unacceptable safety profile encompasses cases such as high occurrence of grade 3 events, occurrence of specific serious adverse event. Unacceptable CMI profile encompasses cases with a pronounced Th₂ response in which there is an isolated elevated IL-13 response, in particular without a response in terms of IFN- γ . The discarding of a group from the selection because of specific safety or CMI reason will be substantiated in the CSR.

If the group(s) ultimately selected for use in upcoming studies for COPD patients is(are) not the one with the highest summary scores at post dose 2 and/or post dose 3, the disqualification of the group(s) with higher summary scores should be adequately justified in the CSR.

The summary scores will be calculated based on the subjects from the ATP cohort.

For each group g , the summary score will summarize how well the group is performing compared to the average active group in terms of the following immunogenicity and CMI results. Before defining the summary score several quantities are introduced (for XX being PD, PE, or PilA):

- GM_{XXg} : the 30 days post last vaccination GMC of Anti- XX of group g
- $AvGM_{XX}$: the 30 days post last vaccination GMC of Anti- XX of all subjects in any active group

Study alias & e-track number(s): NTHI MCAT-001 (201281)

- GM_{CMIXg} : the 30 days post last vaccination GMC of specific Anti-XX CD4+ T cells expressing at least two markers among CD40L, IL-2, TNF-Alpha, IFN-Gamma, IL-13 and IL-17 per million cells of group g
- $AvGM_{CMIX}$ the 30 days post last vaccination GMC of specific Anti-XX CD4+ T cells expressing at least two markers among CD40L, IL-2, TNF-Alpha, IFN-Gamma, IL-13 and IL-17 per million cells of all subjects in any active group

These measures will be transformed in order to be contained between 0 and 1 via the following formulae:

$$D_{XXg} = 1 / (1 + \text{Exp}((AvGM_{XX} - GM_{XXg})/AvGM_{XX}))$$

$$D_{CMIXg} = 1 / (1 + \text{Exp}((AvGM_{CMIX} - GM_{CMIXg})/AvGM_{CMIX}))$$

The following groups will be evaluated at Post-dose 2:

- 10-10-10-AS summary score Post-dose 2
- 10-10-3-AS summary score Post-dose 2

The average GMCs used to calculate the summary scores will be an average of all vaccinated subject from an active group at post dose 2.

The summary score for group g will be computed by taking the weighted geometric mean of the several D measures as follows:

$$D_g = \sqrt[15]{D_{PDg}^4 \times D_{PEg}^4 \times D_{PiLAg}^4 \times D_{CMIPDg}^1 \times D_{CMIPEg}^1 \times D_{CMIPiLAg}^1}$$

A group with a D score of $\frac{1}{2}$ corresponds exactly at the average level of all subjects in the active groups. The highest the value of the summary score for a group, the better the group is performing in terms of immunogenicity and CMI compared to the others.

Differences of less than 0.02 in terms of summary measures will not be considered sufficient to establish a clear hierarchy between 2 groups. Therefore several groups may be considered to be classified as the best ones.

Although these comparisons are exploratory and should be interpreted with caution considering that there is no adjustment for multiplicity, a statistical significance on at least one GMC of the selected antigen is expected to confirm the potential use of the selected active group in future studies.

Study alias & e-track number(s): NTHI MCAT-001 (201281)

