10.6.3.3. Summary score to support dose selection

For each group in Step 2, a summary score at one month post-Dose 2 (Day 90) will summarise how well the group is performing in terms of immunogenicity and CMI results. The calculation of a summary score for both active groups (i.e. 10-10-10-AS and 10-10-3-AS) will be proposed in order to help the formulation selection as a higher summary score indicates a higher global immunogenicity and CMI response.

The summary scores will be calculated based on the subjects from the ATP cohort.

The calculation of these summary scores from immunogenicity data for the interim, and from immunogenicity data and CMI data for the final analyses, and the strategy for their use in the dose selection will be presented more in detail in the Statistical Analysis Plan.

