
1. DOCUMENT HISTORY

Date	Description	Protocol Version
11-MAR-2016	Version 1	Amendment 1 – 30JUL2015
27-JUN-2016	Amendment 1 – Anti-PD cut-off was updated from 100 EL.U/mL to 153 EL.U/mL following the development of the new anti-PD test.	Amendment 1 – 30JUL2015
6-DEC-2016	Amendment 2 – Update the desirability function in order to take into account the Mcat Protein.	Amendment 1 – 30JUL2015

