2. RATIONALE FOR THE AMENDMENT

Summary score's formulas have been updated, taking into account MCat protein according to the rules described in section 7 Statistical Methods.

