3. STUDY DESIGN

The following group names will be used for the statistical analyses:

Group order in tables	Group label in tables	Group definition for footnote	Pooled Groups label in tables	Pooled definition for footnote
1	10-10-10	2 doses of non-adjuvanted NTHI/Mcat vaccine containing 10 mcg of PD, PE-PiA and UspA2		
2	10-10-10-AS	2 doses of AS01E-adjuvanted NTHI/Mcat vaccine containing 10 mcg of PD, PE-PiA and UspA2		
3	10-10-3-AS	2 doses of AS01E-adjuvanted NTHI/Mcat vaccine containing 10 mcg of PD, PE-PiA and 3 mcg of UspA2		
4	PLACE1	2 doses of saline solution – Step 1	Placebo	2 doses of saline solution
5	PLACE2	2 doses of saline solution – Step 2	Placebo	

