$$D_{CMIXXg} = 1 / (1 + \text{Exp}((AvGM_{CMIXX} - GM_{CMIXXg})/AvGM_{CMIXX}))$$

Statistical Analysis Plan

Study alias & e-track number(s): NTHI MCAT-001 (201281)

The following groups will be evaluated at Post-dose 2:

- 10-10-10-AS summary score Post-dose 2
- 10-10-3-AS summary score Post-dose 2

The average GMCs used to calculate the summary scores will be an average of all vaccinated subjects from an active group at post dose 2.

The summary score for group g will be computed by taking the weighted geometric mean of the several D measures as follows:

$$D_g = \sqrt[20]{D_{PDg}^4 \times D_{PEg}^4 \times D_{PilAg}^4 \times D_{UspA2g}^4 \times D_{CMIPDg}^1 \times D_{CMIPEg}^1 \times D_{CMIPilAg}^1 \times D_{CMIUspA2g}^1}$$

A group with a D score of $\frac{1}{2}$ corresponds exactly at the average level of all subjects in the active groups. The highest the value of the summary score for a group, the better the group is performing in terms of immunogenicity and CMI compared to the others.

Differences of less than 0.02 in terms of summary measures will not be considered sufficient to establish a clear hierarchy between 2 groups.

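### The final-analysis dose-selection score (SAP 7.2.3.3) still omits UspA2, the only antigen whose dose differs between the two groups it ranks, and can contradict the Day 90 score on the same data

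*SAP*

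**What the plan says.** The document history of the current SAP (Amendment 2, 6 December 2016) gives the amendment's purpose as "Update the desirability function in order to take into account the Mcat Protein". Section 2 adds: "Summary score's formulas have been updated, taking into account MCat protein according to the rules described in section 7 Statistical Methods". Section 7 holds both places where the score is defined.

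- **7.1.3.3 (analysis up to Day 90).** The antigens are PD, PE, PilA and UspA2. The score is a 20th root, with each antibody term at weight 4 and each CMI term at weight 1, including both UspA2 terms.
- **7.2.3.3 (analysis up to Day 420).** The text is "Before defining the summary score several quantities are introduced (for XX being PD, PE, or PilA". The score is a 15th root with no UspA2 term, the same as in section 6.2.3.3 of the two preceding SAP versions.

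Both sections use GMCs 30 days after the last vaccination, evaluate the groups post-Dose 2, and say that a difference below 0.02 does not establish a ranking. In both, the group with the higher score is the candidate for selection, provided its safety and CMI profiles are acceptable.

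Protocol 10.6.3.3 describes the score as one where "a higher summary score indicates a higher global immunogenicity and CMI response". SAP section 3 defines 10-10-3-AS as "2 doses of AS01E-adjuvanted NTHI/Mcat vaccine containing 10 mcg of PD, PE-PiA and 3 mcg of UspA2"; the protocol gives that UspA2 dose as 3.3 µg. SAP section 10 lists no changes from planned analyses.

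**The concern.** The two scored groups share the same PD dose, PE-PilA dose and adjuvant. The choice between them is a choice of UspA2 dose. A score without UspA2 can differ between them only through antigens dosed identically, that is, through sampling variation or through interference from the UspA2 component.

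Section 9.1 labels the Day 90 analysis as internal and sends the final analysis to the clinical study report and the trial registry. The reported analysis is thus the one with the unamended formula. Two definitions of one quantity, on the same Day 90 samples, could give two different rankings. Nothing in the SAP says which governs. The sponsor's statistician is unblinded from the Day 90 analysis, so a choice made afterwards would be made with the results known.

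**Working it through.** **Inputs from the documents**

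- Component: D = 1 / (1 + exp((Av - GM) / Av)), where GM is the group GMC and Av the GMC over both active groups.
- Weights: 4 per antibody term and 1 per CMI term. Three antigens: 3 × (4 + 1) = 15. Four antigens: 4 × (4 + 1) = 20. Both match the stated roots.
- Group size: about 30 in each group. With equal sizes, Av is the geometric mean of the two group GMCs. A GMC ratio r (10-10-10-AS over 10-10-3-AS) then gives GM/Av = √r in 10-10-10-AS and 1/√r in 10-10-3-AS.
- Decision line: 0.02.

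**Assumed:** the GMC ratios, because the documents give no expected values. CMI ratios are 1 unless stated.

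**Step 1: the SAP's own calibration.** With every ratio equal to 1, each D is 0.5 and both formulas return 0.5000. This agrees with the SAP's statement that a score of one half is the average level.

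**Step 2: only UspA2 differs.** For a UspA2 antibody ratio of 2, GM/Av is 1.414 and 0.707, so D is 0.6021 and 0.4273.

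- 20th root: 0.6021^(4/20) × 0.5^(16/20) = 0.5189, and 0.4273^(4/20) × 0.5^(16/20) = 0.4845. Difference +0.034.
- 15th root: every term is 0.5, so 0.5000 against 0.5000. Difference 0.

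| UspA2 GMC ratio | Day 90 difference (antibody only) | Day 90 difference (UspA2 CMI moves equally) | Final difference |
|---|---|---|---|
| 1.5 | 0.020 | 0.025 | 0.000 |
| 2 | 0.034 | 0.043 | 0.000 |
| 3 | 0.054 | 0.067 | 0.000 |
| 4 | 0.067 | 0.084 | 0.000 |

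The Day 90 score passes 0.02 at a UspA2 ratio of about 1.49, or about 1.38 if UspA2 CMI moves equally. The final score never does.

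**Step 3: opposite rankings.** Take UspA2 3-fold higher in 10-10-10-AS, with PD, PE and PilA antibodies each 10% lower there.

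- Ratio 0.9: GM/Av = 0.9487 and 1.0541, D = 0.4872 and 0.5135.
- Ratio 3: GM/Av = 1.7321 and 0.5774, D = 0.6753 and 0.3959.
- 20th root: 0.4872^(12/20) × 0.6753^(4/20) × 0.5^(4/20) = 0.5228, against 0.4849. Difference +0.038, favouring 10-10-10-AS.
- 15th root: 0.4872^(12/15) × 0.5^(3/15) = 0.4897, against 0.5108. Difference -0.021, favouring 10-10-3-AS.

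Other combinations, with 10-10-3-AS higher on all three NTHi antibodies:

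| NTHi advantage of 10-10-3-AS | UspA2 ratio | Day 90 difference | Final difference |
|---|---|---|---|
| 1.10-fold | 2 | +0.020 | -0.019 (no ranking) |
| 1.15-fold | 2.5 | +0.024 | -0.028 |
| 1.20-fold | 3 | +0.026 | -0.037 |

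**Step 4: how little moves the final score.** A common antibody advantage of about 1.105-fold on PD, PE and PilA takes the 15th-root score past 0.02. If the log10 SD were 0.3 to 0.5 (assumed), the standard error of one antigen's log10 GMC ratio with 30 per group would be SD × √(2/30), or 0.077 to 0.129. Since log10(1.105) = 0.043, that advantage is well under one standard error for a single antigen.

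**The case against.** The case on the other side is that this is an incomplete edit with limited reach.

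- The amendment's intent is plain, and nobody appears to have chosen to leave UspA2 out.
- Section 9.1 says all previous analyses will be reproduced on cleaned data at the final step, so the four-antigen score should appear there too.
- UspA2 remains visible. Section 7.2.3.1 reports seropositivity and GMCs for each assay, and an ANCOVA GMC ratio between exactly these two groups one month after Dose 2.
- The score is advisory. It sits beside the safety and CMI profiles, and the sponsor may pick the lower-scoring group with a justification in the study report. No primary endpoint or error rate depends on it.
- The reversal needs particular inputs. With PD, PE and PilA all 9% lower instead of 10%, the final difference is -0.019 and no ranking is declared. If only two of the three are 10% lower it is -0.014, and if only one, -0.007. With all three 10% lower and a UspA2 ratio of 2, the Day 90 difference is +0.019, also no ranking.

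All of this stands as a limit on impact, and the likelihood of a reversal is not established. It does not remove the defect. Reproducing the Day 90 score would put two conflicting scores in one report with no rule between them. Reporting UspA2 GMCs beside the score does not make the score respond to them. The requirement to justify departing from the higher score could also fall on the wrong group.

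**Conclusion.** The concern holds. As written, the final-analysis score takes no account of the UspA2 response, although UspA2 dose is the only planned difference between the groups it ranks. That follows from the formula and needs no assumption. The size depends on the GMC ratios, which are assumed here, with equal group sizes. A 2-fold UspA2 difference with all else equal gives 0.034 at Day 90 and 0 at the final analysis. A 3-fold UspA2 difference with the three NTHi antibodies 10% lower gives +0.038 and -0.021, on opposite sides and both beyond 0.02. A reversal is possible rather than shown to be likely. The text is wrong as written and should be corrected before the final score is calculated, even though the score is supportive only.

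**What to change.** In SAP 7.2.3.3, define XX as PD, PE, PilA or UspA2. Replace the 15th-root formula with the 20th-root formula of 7.1.3.3, so that the UspA2 antibody term (weight 4) and the UspA2 CMI term (weight 1) enter the final score. State that this single definition applies to both analyses. If a different final score was intended, the SAP should say why and which score governs selection.

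The cost is two corrections of text. No extra data are needed, since the Day 90 score already requires the UspA2 antibody and CMI results, and the formula is already specified in 7.1.3.3.

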8. STATISTICAL CALCULATIONS

The study groups will be defined by treatment actually administered at Dose 1.

Demography

- For a given subject and a given demographic variable, missing measurement will not be replaced.
- Age: Age at the reference activity, computed as the number of units between the date of birth and the reference activity In case of partial dates of any of these 2 dates:
 - 15th of month, If only the day is missing
 - 30th of June, if day and months are missing

Immunogenicity

- For a given subject and the analysis of a given immunogenicity measurement, missing or un-evaluatable measurements will not be replaced.
- A seronegative subject is defined as a subject whose antibody concentration is below the assay cut-off value.
- A seropositive subject is defined as a subject whose antibody concentration is greater than or equal to the assay cut-off value.
- Antibody concentrations below the assay cut-off will be given an arbitrary value of half the assay cut-off for the purpose of geometric mean concentration (GMC) calculation.
- Calculation of the GMCs will be performed by taking the anti-logarithm in base 10 (anti-log10) of the mean of the log10 concentration/titre transformations.
- All confidence intervals (CIs) computed will be two-sided 95% CIs.
- The assay cut-off is the value under which there is no quantifiable result available. For an assay with a specific 'cut_off' , numerical immuno result is derived from a character field (rawres):
 - If rawres is 'NEG' or '-' or '(-)', numeric result= cutt_off/2,
 - if rawres is 'POS' or '+' or '(+)', numeric result = cut_off,
 - if rawres is '< value' and value<=cut_off, numeric result =cut_off/2,
 - if rawres is '< value' and value>cut_off, numeric result =value,
 - if rawres is '> value' and value<cut_off, numeric result =cut_off/2,
 - if rawres is '> value' and value>=cut_off, numeric result =value,
 - if rawres is '<= value' or '>= value' and value<cut_off, numeric result =cut_off/2,
 - if rawres is '<= value' or '>= value' and value>=cut_off, numeric result =value,
 - if rawres is a value < cut_off, numeric result = cut_off/2,

Statistical Analysis Plan

Study alias & e-track number(s): NTHI MCAT-001 (201281)

- if rawres is a value \geq cut_off, numeric result = rawres,
- else numeric result is left blank.

Safety/reactogenicity

- For **solicited symptoms**, the analysis will exclude subjects with missing or un-evaluable measurements (e.g. total analysis of solicited symptoms will include all vaccinated subjects with documented solicited symptom sheets).
- For the **unsolicited symptoms** and concomitant medications/ products/ vaccinations, subjects who did not report unsolicited symptoms/concomitant medications/ products/ vaccinations will be treated as subjects without unsolicited symptoms or concomitant medications/ products/ vaccinations, respectively.
- Note that for all tables described in this section, the way the percentage of subjects will be derived will depend on the event analysed (see table below for details). As a result, the N value will differ from one table to another.

Event	N used for deriving % per subject
Concomitant vaccination	All subjects with study vaccine administered
Solicited general symptom	All subjects with at least one solicited general symptom documented as either present or absent (i.e. symptom screen completed)
Solicited local symptom	All subjects with at least one solicited local symptom documented as either present or absent (i.e. symptom screen completed)
Unsolicited symptom	All subjects with study vaccine administered
Concomitant medication	All subjects with study vaccine administered

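### SAP section 8 gives some one-sided antibody results a serostatus they do not establish: '< value' above the cut-off counts as seropositive, and '> value' or '>= value' below the cut-off counts as seronegative (low priority)

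*SAP*

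**What the plan says.** Section 8 of the current SAP (Amendment 2), under Immunogenicity, defines serostatus on the concentration: "A seropositive subject is defined as a subject whose antibody concentration is greater than or equal to the assay cut-off value", and "A seronegative subject is defined as a subject whose antibody concentration is below the assay cut-off value". For the GMC, "Antibody concentrations below the assay cut-off will be given an arbitrary value of half the assay cut-off". Protocol section 10.5 has the same definitions but no rule for one-sided results.

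The SAP then lists how a number is derived from the raw character result. The lines that matter here are:

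- For a strict upper bound that does not exceed the cut-off: "if rawres is '< value' and value<=cut_off, numeric result =cut_off/2"
- For a strict lower bound that falls short of the cut-off: "if rawres is '> value' and value<cut_off, numeric result =cut_off/2"
- For a strict upper bound that exceeds the cut-off: "if rawres is '< value' and value>cut_off, numeric result =value"
- For non-strict bounds of either kind that reach the cut-off: "if rawres is '<= value' or '>= value' and value>=cut_off, numeric result =value"
- For non-strict bounds of either kind that fall short of it: "if rawres is '<= value' or '>= value' and value<cut_off, numeric result =cut_off/2"

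The last two lines handle '<=' and '>=' together, although they bound the concentration from opposite sides. Any format not on the list gives a blank. Nothing in the list marks a result as undetermined for serostatus, and no sensitivity analysis is planned for such results. The two preceding SAP versions carry the same list in their section 7.

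**The concern.** A result reported as '< 306' for anti-PD (cut-off 153) says only that the concentration is below 306. The rule records 306, a value that the result itself excludes. The SAP offers no other number on which to judge serostatus, so the subject is counted as seropositive. A result '>= 100' is recorded as 76.5, below its own lower bound, and the subject is counted as seronegative.

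Seropositivity rate and GMC are the planned humoral summaries at every visit, overall and within age, smoking and FEV1/FVC strata (SAP sections 7.1.3.1 and 7.2.3.1). The derived values also enter the ANCOVA of the two adjuvanted groups, both as response and as pre-Dose 1 covariate, and the GMCs enter the formulation summary score (section 7.1.3.3).

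**Working it through.** The plan states no figure that depends on this rule, so there is none to reproduce.

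**Inputs.** Cut-offs in EL.U/mL: anti-PD 153, anti-PE 8, anti-PilA 7, anti-UspA2 18 (protocol Table 10; SAP section 8.1). Group sizes: about 15 in Step 1 and about 30 in Step 2 (protocol section 4.1). The score difference too small to rank the groups is anything under 0.02 (SAP section 7.1.3.3).

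**Step 1: apply the rules literally (anti-PD).**

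| Laboratory result | Recorded as | Counted as | Does the result settle serostatus? |
|---|---|---|---|
| '< 153' | 76.5 | seronegative | yes |
| '< 154' | 154 | seropositive | no |
| '< 306' | 306 | seropositive | no |
| '<= 153' | 153 | seropositive | no |
| '> 100' or '>= 100' | 76.5 | seronegative | no |
| '>= 153' | 153 | seropositive | yes |

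Moving the upper bound from 153 to 154 makes the result slightly less informative, yet it doubles the recorded value and reverses the serostatus. The other three assays behave in the same way at the same multiples of their cut-offs.

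**Step 2: size per sample, for '< 2 x cut-off'.**

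- True value below the cut-off, compared with the half-cut-off convention: 306 / 76.5 = 4-fold.
- True value between 153 and 306: at most 306 / 153 = 2-fold, and seropositive is then correct.
- Mirror case: '>= 100' recorded as 76.5 is understated by at least 100 / 76.5 = 1.3-fold. If the true value were 1000 (an assumption), the factor is 1000 / 76.5 = 13.1.

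**Step 3: size per group.** The GMC is the antilog of the mean log, so k affected samples among n multiply it by (recorded / alternative)^(k/n). The alternative here is half the cut-off. The number of affected samples is an assumption, shown as a range.

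| Affected samples | n = 30 | n = 15 |
|---|---|---|
| one '< 2 x cut-off' | 4^(1/30) = 1.047 | 4^(1/15) = 1.097 |
| three '< 2 x cut-off' | 4^(3/30) = 1.149 | 4^(3/15) = 1.320 |
| three '< 10 x cut-off' | 20^(3/30) = 1.349 | 20^(3/15) = 1.821 |

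Against half the bound instead, one '< 2 x cut-off' result gives 2^(1/30) = 1.023 at n = 30. A wrong serostatus moves the seropositivity rate by 1/30 = 3.3 points or 1/15 = 6.7 points. For example, 29/30 (96.7%, exact 95% CI 82.8 to 99.9) becomes 30/30 (100%, CI 88.4 to 100).

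**Step 4: effect on the summary score.** Take the four-antigen formula of section 7.1.3.3, two otherwise equal active groups, and inflation in one group only. With GMCs f and 1, the average is f^(1/2) and each component is D = 1/(1 + exp((average - GMC)/average)). One antibody carries weight 4/20.

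- f = 1.047, one antibody: score difference 0.0023.
- f = 1.35, one antibody: 0.015.
- f = 1.149, all four antibodies: 0.028.

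Only the last exceeds 0.02. It needs about three affected samples in each of four antibodies, all in the same group.

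**The case against.** **Such results may never occur.** The SAP describes the cut-off as the limit below which nothing is quantified, and each assay has one cut-off. The ordinary low result, '< cut-off', is scored sensibly at half of it. The list also covers entries such as 'NEG' and '(+)', so it reads as a general catch-all. A listed format is not evidence that the laboratory will report it. This stands, and it is the main reason for the low priority.

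**The 4-fold figure is a worst case.** It assumes a true value below the cut-off. That also stands, which is why the 2-fold limit is given beside it.

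**Deleting the awkward results could be worse.** This stands too. A '< value' result is informatively low. As an assumed illustration, take 29 subjects with GMC 1000 and one '< 306' whose true score is 76.5:

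- truth: 1000 x (0.0765)^(1/30) = 918
- current rule: 1000 x (0.306)^(1/30) = 961, or +4.7%
- sample blanked: 1000, or +8.9%

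If the other 29 are all positive, the rate is 30/30 under the rule and 29/29 with the sample left out, both 100%. Only a reported count of undetermined results shows the reader what happened.

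**Stronger readings that the documents do not support.** A reader might infer that every '>= value' result is made seronegative. That happens only below the cut-off; at or above it the result is correctly positive. A reader might also infer that the list contradicts the serostatus definitions or the rule against replacing un-evaluable results. The definitions refer to concentration, the list says how a concentration is obtained, and nothing classes a one-sided result as un-evaluable. This is crude imputation, not a contradiction of the text.

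**Conclusion.** The point holds in a limited form. For '< value' with the bound above the cut-off, '<= value' with the bound at or above it, and '> value' or '>= value' with the bound below it, the SAP assigns a serostatus that the laboratory result does not establish. This follows from the quoted lines and the definitions, on the inference that serostatus is read from the derived number.

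The impact is conditional. The frequency is not stated and may be nil. Each affected upper-bound result pushes the GMC upward, but '> value' at or above the cut-off is scored at its lower bound and pushes it down, so the net direction depends on the mix.

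It may be tempting to conclude that the choice between 10-10-10-AS and 10-10-3-AS is at risk. The documents do not show that. One affected sample shifts the score by about 0.0023 against 0.02, the rule is the same in every group, and the testing laboratory is blinded (protocol section 5.3). The analyses concerned are secondary and descriptive or exploratory. Priority: low.

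**What to change.** In SAP section 8:

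1. Split the combined '<=' / '>=' lines so that upper and lower bounds are handled separately.
2. For any one-sided result whose bound does not settle serostatus, set serostatus to undetermined, leave it out of the seropositivity rate, and list the number by assay, group and visit.
3. Leave '> value' or '>= value' with the bound below the cut-off blank instead of scoring half the cut-off.
4. Do not simply delete '< value' or '<= value' results that do not settle serostatus from the GMC or ANCOVA. Treat them as interval-censored between 0 and the bound, or at least report a sensitivity analysis that scores them at half the cut-off and at the bound.

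The cost is a few derivation lines and a small sensitivity analysis. A few serostatus results become undetermined. A lower-bound result left blank at Day 0 removes that subject's ANCOVA covariate for the antibody. One left blank at Day 90 could affect according-to-protocol membership if no other assay result exists. If no such results occur, nothing changes.
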